19.0 Provisions to Protect the Privacy Interests of Subjects

- *Describe the steps that will be taken to protect subjects' privacy interests. "Privacy interest" refers to a person's desire to place limits on whom they interact or whom they provide personal information.*

PROTOCOL TITLE: Assessment of Sous Vide Water Baths for Acute Rewarming of Frostbitten Extremities.

- Patients who may meet the enrollment criteria will be approached and asked if they are willing to learn about a research study taking place that they may qualify for. If the patient is not interested they will receive the current standard of care treatment.
- *Describe what steps you will take to make the subjects feel at ease with the research situation in terms of the questions being asked and the procedures being performed. “At ease” does not refer to physical discomfort, but the sense of intrusiveness a subject might experience in response to questions, examinations, and procedures.*
- Potential subjects will have the traditional method of rewarming explained as well as an explanation of how SVR works. They will be informed that research is voluntary and they can withdraw at any point.
- *Indicate how the research team is permitted to access any sources of information about the subjects.*
- The study team will be permitted to access the emergency department chart of the consented subjects to be able to record de-identified sex, age, frostbite location, further information about the case or any adverse event, and patient outcomes. The subject provides consent for this access as part of the informed consent process.

20.0 Economic Burden to Subjects

- *Describe any costs that subjects may be responsible for because of participation in the research.*
- Hot water burns or electrical failure causing injury and the treatment of such injuries would be the only foreseeable costs incurred by the patient. The burn risk is present in the traditional method of frostbite rewarming and the SVR is expected to minimize this risk. Biomedical engineering at Dartmouth-Hitchcock has assessed the SVD, deemed it low risk, and cleared it for use.

21.0 Consent Process

- *Indicate whether you will you be obtaining consent, and if so describe:*
- *Where will the consent process take place*

PROTOCOL TITLE: Assessment of Sous Vide Water Baths for Acute Rewarming of Frostbitten Extremities.

- Patient interest in study participation will be determined in the emergency department exam rooms (not the waiting room) by the provider. Patient consent will then be obtained in emergency department exam room by the investigator.
- Upon patient consent, the researcher will approach the provider to obtain consent. Provider consent will occur in the participating emergency departments in a separate location outside of the patient's exam room. The SVR will not proceed without patient consent, therefore, provider consent will be obtained only once patient consent has been obtained.
- *Any waiting period available between informing the prospective subject and obtaining the consent.*
 - None. The prospective subject will be identified and consented at the earliest convenience as to avoid delaying emergency department rewarming. If providers are unable to reach an on-call investigator and determine their availability within 20 minutes from the patient expressing interest in the study, standard rewarming will proceed via traditional water exchange practices.
- *Any process to ensure ongoing consent.*
 - Upon initial consent, the subject will be informed that they are able to withdraw from the study at any point during the rewarming period.
- *Whether you will be following "SOP: Informed Consent Process for Research (HRP-090)." If not, describe:*
 - SOP: Informed Consent Process for Research (HRP-090) will be followed.

Non-English Speaking Subjects

- Inability to understand and speak English are exclusion criteria for this study.

Subjects who are not yet adults (infants, children, teenagers)

- *Describe the criteria that will be used to determine whether a prospective subject has not attained the legal age for consent*

PROTOCOL TITLE: Assessment of Sous Vide Water Baths for Acute Rewarming of Frostbitten Extremities.

to treatments or procedures involved in the research under the applicable law of the jurisdiction in which the research will be conducted. (E.g., individuals under the age of 18 years.)

- *Describe whether parental permission will be obtained from:*
 - *One parent even if the other parent is alive, known, competent, reasonably available, and shares legal responsibility for the care and custody of the child.*
 - a. All subjects age 18 and overall will be asked to provide informed consent.
 - b. All subjects ages 7-17 will be asked to provide assent in addition to consent of one parent or legal guardian.
- All subjects ages 2-6 will be enrolled if consent of one parent or legal guardian is provided. *Describe whether permission will be obtained from individuals other than parents, and if so, who will be allowed to provide permission. Describe the process used to determine these individuals' authority to consent to each child's general medical care.*
 - If a parent or legal guardian is not present to provide consent, patients under age 18 will be excluded.
- *Indicate whether assent will be obtained from all, some, or none of the children. If assent will be obtained from some children, indicate which children will be required to assent.*
 - Subjects age 7-17 will be asked to provide assent.
 - A prepared assent form using more simple language, but mirroring the adult consent, will be used as the basis to provide information to the subject aged 7-17 and for the assent process.
 - Subjects under age 7 will not be asked to provide assent.
- *When assent of children is obtained describe whether and how it will be documented.*
 - Confirmation off assent will be recorded in the appropriate location on form HRP-502 and comply with SOP HRP-091

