4.0 Study Endpoints*

- The primary study endpoint will be the rewarming of frostbitten extremities for 30 minutes at 38°C.
- The secondary study endpoint will be a survey regarding ease of use of this rewarming modality.
- The primary safety endpoint will be patient pain or discomfort that is determined to be unrelated to the discomfort known to be associated with rewarming frostbitten tissue. Two consecutive temperature measurements above 42°C will prompt the cessation of the SVR.

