6.0 Procedures Involved*

- Patients presenting to the ED at Dartmouth-Hitchcock and external study sites with acute frostbite (tissue still frozen) of the hands and/or feet will be identified and approached for recruitment. Patients not entering the study will continue to be treated by ED providers in the traditional fashion.
- Patients recruited for the SVR study will be consented to have their circulating warm water bath(s) heated by the novel SVR method. Providers or nurses caring for the study subjects will be consented to participate and will 1) conduct the SVR procedure, and 2) complete a questionnaire. A researcher will gather SVR equipment and attach two thermometers on the basin: one on the side nearest the SVD, the other on the opposite side. The researcher will verbally walk the provider or nurse carrying out the SVR through the following steps. A 15 L Sterilite® basin will be filled to the marked line (12cm) with water from jugs at room temperature, for each frozen extremity. One extremity can be rewarmed in a single basin, with the possibility for up to four simultaneous SVR basins for a patient with frostbite of all hands and feet. The SVD will be attached to the distal edge of the basin, with one SVD per rewarming basin. The SVD will be turned on and set to maintain the bath at a constant 38°C for 30 minutes duration. The thermometers will be powered on continuously and the researcher will record temperatures simultaneously from each thermometer and the SVD every 2 minutes. At the end of the 30 minute treatment, the extremity will be assessed by the researcher for warmth and pliability. If the extremity still feels cold or frozen, an additional 30 minutes in the water bath will commence, with

PROTOCOL TITLE: Assessment of Sous Vide Water Baths for Acute Rewarming of Frostbitten Extremities.

subsequent reassessment. Rewarming will be considered complete when the affected tissue becomes red or purple, soft, and pliable.

- Patients who do not consent to SVR and elect for traditional water bath management will be asked for their consent to record the similar demographic, water temperature, and time-to rewarm data as in the SVR treatment arm. After re-warming is complete, the provider will be asked to fill out a survey regarding the ease of use and efficacy of the SVR.
- *Describe:*
 - *Procedures performed to lessen the probability or magnitude of risks.*

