 - The blood pressure cuff used in the standard emergency department assessment of vital signs will be placed on an extremity that is not currently being rewarmed, whenever possible, to avoid constricting blood flow to the affected tissue.
- *Data Collection:*
 - Prior to rewarming, physical examination of the patient, including the frozen extremity, will be completed and documented in the EPIC/EMR chart by the provider.
 - Two thermometers, placed in the rewarming basin, will continuously monitor the water temperature. The temperature reading on both thermometers as well as the SVD will be recorded on a paper data sheet by a trained provider at 2-minute intervals until the 30 minutes of treatment are complete.

PROTOCOL TITLE: Assessment of Sous Vide Water Baths for Acute Rewarming of Frostbitten Extremities.

- The researcher will repeat an exam, assessing all extremities being treated by SVR, at 30 minutes to determine warmth and pliability of the tissue, confirming thaw. Rewarming will be considered complete if the affected tissue becomes red or purple, soft, and pliable. The same rewarming criteria applies for all extremities.
 - The provider will be asked to fill out a survey on all acute frostbite patients whom consent to the study protocol, as well as those that do not.
 - *The source records that will be used to collect data about subjects. (Attach all surveys, scripts, and data collection forms.) If there are plans for long-term follow-up (once all research related procedures are complete), what data will be collected during this period.*
 - The patient's age and sex will be recorded. The physical examination and pertinent medical information will be reviewed to confirm the location and extent of the frostbite and for contributing conditions.
 - Demographics and relevant medical history will be accessed.
 - Please see attached surveys and data collection forms.
 - Enrolled subjects may be contacted via phone and myDH or local electronic medical record communication at 6 months post-enrollment to assess long term outcomes of their frostbite. Chart review to assess related complications will also occur at this time.
 - *Explain if any part of this study involves genetic analysis of biological specimens. If yes, explain whether the study is based on one the following:*
 - This study does not involve genetic analysis of biological specimens.

Provider Participation:

- *Role/Activities:*

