PROTOCOL TITLE: Assessment of Sous Vide Water Baths for Acute Rewarming of Frostbitten Extremities.

- Providers assigned to a patient in the emergency department who is determined to have acute frostbite will be targeted.
- The provider's role will be to identify an acute frostbite patient and ask their patient whether they would be interested in hearing more about and potentially participating in a study assessing a new way to rewarm their frostbitten tissue.
- If the patient agrees, the provider access the study on-call investigator list (posted in the ED provider area) and inform a researcher of the patient and need to discuss the stud and potentially enroll the patient.
- *Recruitment:*
 - Providers assigned to a patient in the emergency department who is determined to have acute frostbite.
- *Eligibility:*
 - Any provider managing a frostbite patient at the training levels of PA, APRN, resident physician, fellow, or attending physician are eligible.
- *Consent Process:*
 - Once the patient has consented to participate, the provider will be consented in an area of the emergency department separate from the patient's room, using the provider consent form.
- *Risks/Benefits:*
 - Risks to providers should be minimal. We do not anticipate providers having any difficulty with voluntary decision-making for this study.
 - Benefits to the provider may include improved work flow due to the decreased labor in maintaining a SVR water bath in comparison to manual water bath management. Additionally, participation will provide a firsthand opportunity to treat acute frostbite with a new modality that has potential for increased use in the future.
- *Data Collection:*
 - After successful completion of the SVR, providers will be asked to take a short, 6-question paper survey regarding ease-of-use of the SVR.

PROTOCOL TITLE: Assessment of Sous Vide Water Baths for Acute Rewarming of Frostbitten Extremities.

- Paper data collection forms will be kept in a locked office until transferred by the PI to a Microsoft excel file on a password-protected DH computer.

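### The protocol conflicts on who completes the ease-of-use survey, its only secondary endpoint, and does not limit the summary to providers who used the device

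*Combined protocol and SAP*

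**What the plan says.** Section 4.0 sets the endpoint: "The secondary study endpoint will be a survey regarding ease of use of this rewarming modality". Three statements in Section 6.0 then bear on who answers the survey.

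- The procedures text has a bullet on patients who decline the device. It begins "Patients who do not consent to SVR and elect for traditional water bath management will be asked for their consent to record the similar demographic" and ends by saying that, once rewarming is complete, "the provider will be asked to fill out a survey regarding the ease of use and efficacy of the SVR".
- Under Data Collection, the provider is to be "asked to fill out a survey on all acute frostbite patients whom consent to the study protocol, as well as those that do not".
- Under Provider Participation, the rule is narrower: "After successful completion of the SVR, providers will be asked to take a short, 6-question paper survey regarding ease-of-use of the SVR".

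On consent, Section 6.0 (Provider Participation) says "Once the patient has consented to participate, the provider will be consented in an area of the emergency department separate from the patient's room". Section 21.0 says "provider consent will be obtained only once patient consent has been obtained" and gives as its reason that SVR does not go ahead without the patient's agreement.

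Section 17.0 promises descriptive statistics for the provider assessment of ease of use. It does not say whose assessments are included. Section 14.0 stops all further data collection once a subject is withdrawn.

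**The concern.** The three survey rules cannot all be followed, and each gives a poor endpoint if followed alone. Under the broad rule, a provider who ran a manual bath rates a device not used on that patient. Under the narrow rule, providers whose SVR run was stopped or failed are never asked, although their view of usability is among the most informative. A site must pick one rule. With 5 to 10 additional locations anticipated (Section 1.0), sites may pick differently, and the summary would then describe no defined population.

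The consent sequence adds a second gap. It is built around patients who accept SVR, so it is unclear on what footing a manual-bath provider's survey is collected.

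**Working it through.** The documents give no figure for this endpoint, and Section 12.0 states that there is no sample size calculation. The check is therefore a comparison of passages, followed by two illustrations on assumed inputs.

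**Who is surveyed**

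| Place | Manual-bath provider | SVR completed | SVR stopped or failed |
|---|---|---|---|
| 6.0, bullet on patients who decline | Yes, on a literal reading | Not addressed in that bullet | Not addressed in that bullet |
| 6.0, Data Collection | Yes | Yes | Yes, by implication |
| 6.0, Provider Participation | No | Yes | No |
| 14.0, after withdrawal | Not applicable | Not applicable | Arguably no, since collection ends |

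Stopped runs are foreseen: Sections 4.0, 6.0, 14.0 and 15.0 all describe circumstances in which SVR ceases. The last column is therefore not empty by design.

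**Provider consent**

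- Patient accepts SVR: provider consent follows. The route is clear.
- Patient declines SVR but allows data recording (Section 6.0, where these patients form the control group): patient consent of a kind exists. Whether it opens provider consent is not stated.
- Patient declines everything: no provider route is stated. Section 6.0 has the provider call a researcher only if the patient is willing to hear more, and Section 19.0 sends an uninterested patient to standard care. The Data Collection sentence nevertheless still asks for a survey.

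**Illustration 1: pooling non-users.** Let r be the share of surveys from non-users, p_u the proportion of users answering easy, and p_n the same for non-users.

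Pooled proportion = (1 − r) × p_u + r × p_n

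Assume p_u = 0.90 and one survey per patient.

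| r | p_n = 0 | p_n = 0.5 | p_n = 1 |
|---|---|---|---|
| 0.10 | 0.81 | 0.86 | 0.91 |
| 0.20 | 0.72 | 0.82 | 0.92 |
| 0.50 | 0.45 | 0.70 | 0.95 |

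For r = 0.20 and p_n = 0: 0.80 × 0.90 + 0.20 × 0 = 0.72. If only users are analysed, the figure stays at 0.90.

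**Illustration 2: leaving out stopped runs.** Let f be the share of SVR runs stopped or failed, p_c the proportion answering easy after completed runs, and p_f the same after stopped runs.

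Excess from surveying completed runs only = f × (p_c − p_f)

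Assume f = 0.20 and p_c = 0.90.

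- p_f = 0.5: 0.20 × 0.40 = 0.08, so 90% is reported against 82% for all operators.
- p_f = 0: 0.20 × 0.90 = 0.18, so 90% is reported against 72%.

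The direction favours the device whenever p_f is below p_c.

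**The case against.** The best reply is that the most specific text, under Provider Participation, already confines the SVR survey to SVR users. The Data Collection sentence says only that there is a survey and does not give its content. The sentence that names SVR may be a general closing step that happens to sit at the end of the bullet on patients who decline. Section 6.0 refers to attached surveys in the plural. These were not available for review and may include a form for the manual method. The mention of success may also be meant as timing and not as a filter. All of this is possible, but none of it is written down, and the three sentences still disagree.

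Three stronger readings are tempting, and the documents do not support them.

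- A reader might infer that manual-bath providers cannot be consented at all. The sequencing clauses require patient consent without specifying consent to SVR, and control patients do consent to data recording. A route may exist for them. The clear gap is the patient who declines all participation.
- A reader might infer that the endpoint will be contaminated. Section 17.0 states no pooling. It fails to exclude it, so mixing is possible and not planned.
- A reader might try to count the affected surveys by taking a refusal share of the 20 cases at the top of the range in Section 2.0. No refusal share is given, and that range of 5 to 20 counts device-treated cases, so refusals would come on top. For U device cases the added surveys would be U × r/(1 − r). With U = 20 that is 2.2 at r = 0.10 and 13.3 at r = 0.40. With U = 5 it is 0.6 and 3.3. The spread shows that no useful count can be derived.

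There is also a fair objection to the remedy: surveying providers after stopped runs meets the Section 14.0 limit on data collection after withdrawal. That limit has to be addressed explicitly.

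**Conclusion.** The point stands as an internal conflict over the population for the only secondary endpoint. Section 6.0 gives incompatible rules: the broad one admits ratings from providers who did not use SVR for that patient, and the narrow one omits stopped or failed SVR and would tend to favour the device. Section 17.0 does not resolve it. The provider consent route is unstated where the patient declines everything and unclear where the patient gives data-only consent.

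The size cannot be derived from the documents. The figures of 72% to 92% for pooling, and of 8 to 18 percentage points for omitting stopped runs, rest on assumed values (90% of users or completed runs rated easy, a 20% share of non-users or stopped runs). They show only that either choice could matter in a study this small. The conclusion also depends on the text alone, since the survey forms could not be seen. If a separate manual-method form exists, the protocol should still say who receives it. The consent gap by itself would be a drafting matter. What lifts the point above that is the undefined endpoint population, together with the selection built into the narrow rule.

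**What to change.** Reconcile the three survey statements in Section 6.0 with each other and with Section 21.0.

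1. Define the secondary endpoint population as consented providers who carried out SVR, including runs that were stopped or did not succeed. Replace the success condition in Provider Participation accordingly.
2. State in Section 14.0 that the provider's survey is still collected when the patient's SVR ends early, despite the general limit on data collection after withdrawal.
3. For manual-bath patients, either drop the survey or reword it so that it rates the manual method. If it is kept, state in Sections 6.0 and 21.0 that provider consent may follow the patient's data-only consent. Where the patient declines everything, take no survey unless a separate provider consent route is written in.
4. State that any manual-method survey is reported separately and does not enter the SVR ease-of-use summary.

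The cost is wording in Sections 6.0, 14.0 and 21.0, a sentence on separate reporting in Section 17.0, and possibly one alternate survey header. Enrolment and the SVR procedure are unaffected.

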22.0 Process to Document Consent in Writing

This study will comply with SOP: Written Documentation of Consent (HRP-091) when the patient is physically able to sign the consent documentation.

PROTOCOL TITLE: Assessment of Sous Vide Water Baths for Acute Rewarming of Frostbitten Extremities.

We are requesting an alteration on the documentation of informed consent for subjects who are physically unable to sign. The consent process will remain unchanged from section 21.0 of this document, however given the enrolling population it is feasible if not expected that some potential subjects will present with bilateral frostbite of the hands and be physically unable to sign for themselves.

In cases where the patient is unable to legibly initial, sign and date, due to injury to the hands, but is able to make a mark on the page, the patient will make a mark on/near the line for initials and the place for signature. A witness who is an impartial third party will observe consent discussion and the marking of the consent. The witness will acknowledge that they saw the subject make his mark on the specific date and then sign, print name, and date the witness section of the consent form.

In instances where the patient is unable to make any mark on the consent form we will obtain and document verbal consent from the patient on the consent form and have an impartial third party serve as witness to the consent process. The person obtaining consent will sign and date the consent form. The witness will acknowledge that the informed consent was fully explained and the subject understood the study details. The witness will sign, print name, and date the witness section of the consent form.

Only one consent form will be used for up to four extremities being treated for frostbite using the SVR rewarming process detailed in this document.

